5.2.3 Follow-Up Period

Assessments performed during hospital discharge and the follow-up period are summarized below. The detailed schedule of study procedures and events is presented in [Appendix 2](#).

5.2.3.1 Hospital Discharge and Follow Up Visits (DAY 21 [+1 DAY], AND DAYS 28 [+ 2 DAYS], 60 [+ 2 DAYS], 90 [+ 2 DAYS])

After the treatment, all the subjects will be followed up at Hospital Discharge (if applicable) and on Days 21[+1 Day], and Days 28 [+2 Days], 60 [+2 Days], 90 [+2 Days].

For both treatment groups, the following will be measured and recorded at all visits: vital signs, full physical examinations, ascites assessment, HE assessment, hemodynamic assessment, peripheral oxygen saturation, blood sample, ACLF grade, illness severity scoring (CLIF-C OF score, CLIF-C ACLF score, Child-Pugh score and MELD score), prior and concomitant medications, AEs, data on liver transplantation, subject survival and cause of death.

All subjects who remain in the hospital will continue to have treatment period assessments performed up through Hospital Discharge. Follow-up assessments for Days 21, 28, 60, and 90 will be performed for all subjects.

At Days 28 and 90, data on liver transplant, subject survival and cause of death will be measured and recorded.

5.2.4 Follow-Up for Early Discontinued Subjects Withdrawn from the Study

Subjects who withdraw from the study early should have all Day 90 procedures performed at the time of withdrawal (preferably within 1 week of withdrawal) and will include: vital signs, full physical examinations, ascites assessment, HE assessment, hemodynamic assessment, peripheral oxygen saturation, blood sample, ACLF grade, illness severity scoring (CLIF-C OF score, CLIF-C ACLF score, Child-Pugh score and MELD score), prior and concomitant medications, AEs, data on liver transplantation, subject survival and cause of death.

If a subject receives a liver transplant, study treatment and all treatment related assessments will be discontinued upon transplant. The criteria to determine when a subject becomes a candidate for liver transplantation is described in protocol section 5.3.2.1. The subject will continue to have Days 21, 28, 60, and 90 follow-up procedures performed.

Subjects with any one of the severe AEs listed in protocol section 5.3.2 will be discontinued from study treatment and all treatment-related assessments and should continue to have subsequent planned visit assessment procedures performed.

5.3 Treatment Administration

5.3.1 PE-A 5% Dosage, Procedures, and Treatment Regimen

Plasma exchange treatment (PE-A 5%) will be performed using 5% albumin solution (Albutein 5%). Fresh frozen plasma will be administered after the 5% albumin administration to prevent coagulopathy, and the PE-A 5% session is considered completed at the end of the FFP administration. In subjects without severe coagulopathy (INR ≤ 3), two-thirds of the volume exchanged will be replaced with albumin 5% and one-third with FFP. In subjects with severe coagulopathy (INR >3), half of the volume exchanged will be replaced with albumin and half with FFP.

One-point-two (1.2) plasma volumes will be exchanged per PE-A 5% session. Total blood volume (TBV) will be calculated according to Nadler's formula. Plasma volume will be estimated from the calculated TBV and the Hematocrit (HCT). The volume to be exchanged will be considered as the volume to be infused (not the fluid to be removed).

A minimum of 4 and a maximum of 9 PE-A 5% sessions (maximum treatment period: 17 days) will be performed in each subject. The number of PE-A 5% sessions will be determined by the pattern of response (complete response, no response, or partial response) to PE-A 5% treatment (Table [5-1](#) and Table [5-2](#)) and is described briefly below:

Treatment schedule consists of 2 initial PE-A 5% sessions on consecutive days followed by every other day PE-A 5% sessions. The aim of the intervention is to achieve complete response (resolution of ACLF or improvement to ACLF-1a):

- Subjects with very early complete response after 1 or 2 PE-A 5% sessions (resolution of ACLF or improvement to ACLF-1a) will receive 3 or 2 additional PE-A 5% sessions, respectively, to consolidate the response because the total number of PE-A 5% sessions should not be lower than 4. See Table 4-1 for details.
- Subjects with very early complete response after 3 PE-A 5% sessions (resolution of ACLF or improvement to ACLF-1a) will receive 2 additional PE-A 5% sessions to consolidate the response.
- Subjects with complete response after 4 PE-A 5% sessions (resolution of ACLF or improvement to ACLF-1a) will receive 2 additional PE-A 5% sessions to consolidate the response. See Table 4-1 for details in the protocol.
- Subjects with no response (subject with no change or worsening of ACLF grade) after 4 PE-A 5% sessions will discontinue treatment so the total number of PE-A 5% sessions will be 4.
- Subjects with partial response after the first 4 PE-A 5% sessions (reduction of 1 organ failure or more to ACLF-1b or ACLF-2) will be treated accordingly: as described below:
 - Subjects with partial response who in the course of the additional PE-A 5% sessions show complete response will receive 2 consolidating sessions after achieving complete response. See Table 4-2 for details.
 - Subjects with partial response who in the course of the additional PE-A 5% sessions worsen to ACLF-3b will be discontinued for the PE-A 5% sessions.
- In summary, regardless of the type of response, the total number of sessions should never be lower than 4 or higher than 9.

IVIgs will be administered intravenously at a dose of 200 mg/kg 1 day after every 2 PE-A 5% sessions in order to prevent the development of hypogammaglobulinemia and infection. In those subjects receiving an odd number of PE-A 5% sessions (e.g., #5, #7, or #9 PE-A 5% sessions when they are the last PE session for the subject), IVIGs will be administered 1 day after this PE-A 5% session at a dose of 100 mg/kg. Initial infusion rate of IVIGs will be of 0.5 mL/kg/hour, increasing to a maximum rate of 2 mL/kg/hour if tolerance is adequate. Refer Table [5-1](#) and Table [5-2](#) details.

Instituto Grifols, S.A. / Protocol IG1407

The entire study duration including follow-up period will be 90 days after randomization.

5.3.2 Standard Medical Treatment

Standard medical treatment will be administered per institution standards. Subject's treatment period will be 7 days for all subjects and will be prolonged, depending on subject's ACLF evolution, to up to 17 days:

- Subjects in the SMT group with ACLF-1b, -2, or -3a who achieve complete response (ACLF resolution or improve to ACLF-1a) within the treatment period (from Day 1 to Day 7), will be assessed for 4 more days after the ACLF resolution or improvement and then will be followed up at Hospital Discharge (if applicable) and on Days 21, 28, 60, and 90.
- Subjects in the SMT group with ACLF-1b, -2, or -3a who experience no response (maintain or worsen their ACLF grades) throughout the treatment period (from Day 1 to Day 7), will be further assessed for up to Day 17 and will be then followed up at Hospital Discharge (if applicable) and on Days 21, 28, 60, and 90.

The entire study duration including follow-up period for subjects who receive SMT will be 90 days after randomization.

5.4 Study Variables

5.4.1 Efficacy Variables

The following efficacy variables will be assessed in this study:

- **Primary Efficacy**
 - Time to death through Day 90 after randomization of SMT+PE-A 5% versus SMT alone
- **Secondary Efficacy**
 - Time to liver transplant or death through Day 90 after randomization of SMT+PE-A 5% versus SMT alone
 - Time to death through Day 28 after randomization of SMT+PE-A 5% versus SMT alone
- **Exploratory Efficacy**
 - Time to death through Day 90, time to transplant or death through Day 90, and time to death through Day 28 after randomization in subgroups of subjects with ACLF-1b, ACLF-2, or ACLF-3a
 - Time to death and time to transplant or death through in-patient hospital stay (including ICU stay) in the entire study population and in the subgroups of subjects with ACLF-1b, ACLF-2, or ACLF-3a
 - Time to transplant or death through Day 28 after randomization in the entire study population and in the subgroups of subjects with ACLF-1b, ACLF-2, or ACLF-3a
 - Incidence of individual organ failures: liver, renal, brain, coagulation, circulation, and respiration, as defined by the CLIF-C OF score and the total CLIF-C OF score, during the treatment period and at the end of treatment, and of hospitalization (or liver transplantation or death)
 - ACLF course (resolution, improvement, steady course, or worsening), CLIF-C ACLF score, Child-Pugh score, and MELD score
 - Systemic inflammation as measured by CRP, WBC, and procalcitonin
 - Rate of all new infections
 - Time-to-hospital discharge
 - Albumin levels in serum measured pre and post PE-A 5% to monitor the status of infused albumin in subjects during the course of the study

Instituto Grifols, S.A. / Protocol IG1407

- Ascites Assessment

5.4.2 Safety Variables

The following safety variables will be assessed in this study:

- **Main Safety Variables**

- The number of suspected adverse drug reactions (ADRs), and adverse reactions (ARs), and incidence rates of subjects with suspected ADRs and ARs for the study period and within 72 hours after PE-A 5% completion (or after PE-A 5% stops).
- The number and incidence rate of overall AEs and Serious Adverse Event(s) (SAEs), as well as deaths and discontinuations due to AEs will be also collected and analyzed.
- According to the investigator's assessment, all clinically relevant changes in vital function and laboratory testing parameters findings will be considered AEs.

- **Other Safety Variables:**

- Vital signs (temperature, blood pressure, heart rate, respiratory rate) recorded at each scheduled visit and in particular before and after each PE-A 5% session
- Clinical laboratory test parameters (blood cell counts, platelet count, INR, fibrinogen, etc.)
- Physical examinations

6 General Statistical Considerations

All analyses will be conducted using SAS Version 9.4 or higher.

Unless otherwise noted, for continuous variables, descriptive statistics for continuous/quantitative data will include the number of non-missing values, mean, standard deviation, median, 25th percentile (Q1), 75th percentile (Q3), minimum, and maximum. In general, the mean, median, Q1 and Q3 will be presented to one decimal place greater than the original data, and the minimum and maximum will have the same number of decimal places as the original data. For categorical/qualitative data, descriptive statistics will include counts and percentages per category.

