
GRIFOLS
 
Bioscience Industrial Group
	
Number
 
BIG-CL-PRT-000002
 
IG1407 - Effects of Plasma Exchange with Human Serum Albumin 5% (PE-A 5%) on Short-term Survival in Subjects with "Acute-On-Chronic Liver Failure" (ACLF) at High Risk of Hospital Mortality
	
Version
 
6.0
	
Status
 
Retired
	
Effective Date
 
29-Mar-2023
	
Page
 
41 of 102

The Treatment Period will be up to 17 days. See [Appendix 1](#) and [Appendix 2](#) for detailed study schedules.

Subjects in both the SMT+PE-A 5% treatment group and the SMT control group will be followed for 90 days after randomization. During the entire study, the safety of both groups will be monitored by a DSMB ([Section 1](#)).

The overall study schema is shown in [Figure 4-1](#).

[figure not shown]

Figure 4-1 Overall Study Schema

FU = follow up visit

IVIGs will be administered intravenously at a dose of 200 mg/kg 1 day after every 2 PE-A 5% sessions in order to prevent the development of hypogammaglobulinemia and infection. For subjects ending the treatment at an odd-number PE session (eg, #5, #7, or #9), IVIGs will be administered at a dose of 100 mg/kg 1 day after this last PE session. Initial infusion rate of IVIGs will be of 0.5 mL/kg/hour, increasing to a maximum rate of 2 mL/kg/hour if well tolerated.

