6.1.1.3 PE-A 5% Treatment Regimen

A minimum of 4 and a maximum of 9 PE-A 5% sessions will be performed in each subject. The number of PE-A 5% sessions will be determined by the pattern of response (complete response, no response, or partial response) to PE-A 5% treatment ([Table 6-1](#) and [Table 6-2](#)) and is described briefly below:

Treatment schedule consists of 2 initial PE-A 5% sessions on consecutive days followed by every other day PE-A 5% sessions. The aim of the study is to achieve complete response (resolution of ACLF or improvement to ACLF-1a):

- Subjects with very early complete response after 1 or 2 PE-A 5% sessions (resolution of ACLF or improvement to ACLF-1a) will receive 3 or 2 additional PE-A 5% sessions, respectively, to consolidate the response because the total number of PE-A 5% sessions should not be lower than 4. See [Table 6-1](#) for details.
- Subjects with very early complete response after 3 PE-A 5% sessions (resolution of ACLF or improvement to ACLF-1a) will receive 2 additional PE-A 5% sessions to consolidate the response.

- Subjects with complete response after 4 PE-A 5% sessions (resolution of ACLF or improvement to ACLF-1a) will receive 2 additional PE-A 5% sessions to consolidate the response. See [Table 6-1](#) for details.
- Subjects with no response (subject with no change or worsening of ACLF grade) after 4 PE-A 5% sessions will discontinue treatment so the total number of PE-A 5% sessions will be 4.

Table 6-1 PE Schedule (Number of Sessions) according to the Clinical Response to Treatment (Complete and No Clinical Responses)

Very early complete clinical response after the first 1 or 2 PE sessions ^a											
PE	▲ #1	▲ #2	■	▲ #3		▲ #4	■				
Day	1	2	3	4	5	6	7				
Very early complete clinical response after the first 3 PE sessions ^b											
PE	▲ #1	▲ #2	■	▲ #3		▲ #4	■	▲ #5	●		
Day	1	2	3	4	5	6	7	8	9		
Complete clinical response after the first 4 PE sessions ^c											
PE	▲ #1	▲ #2	■	▲ #3		▲ #4	■	▲ #5		▲ #6	■
Day	1	2	3	4	5	6	7	8	9	10	11
No clinical response after the first 4 PE sessions ^d											
PE	▲ #1	▲ #2	■	▲ #3		▲ #4	■				
Day	1	2	3	4	5	6	7				

- ^a These subjects will receive 3 or 2 additional PE-A 5% sessions following complete clinical response and therefore will receive a total of 4 PE-A 5% sessions.
- ^b These subjects will receive 2 additional PE-A 5% sessions following complete clinical response and therefore will receive 5 PE-A 5% sessions.

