8 ASSESSMENT OF SAFETY

8.1 Safety Variables

- The number of suspected ADRs, including adverse reactions (ARs), and incidence rate of subjects with suspected ADRs during the treatment period and within 72 hours after PE-A 5% completion (or after PE-A 5% stops) will be considered as the main safety variables. The number and incidence rate of overall AEs and SAEs, as well as deaths and discontinuations due to AEs will be also collected and analyzed.
- Vital signs will be recorded at each scheduled visit and in particular before and after each PE-A 5% session.
- Clinical laboratory test parameters (blood cell counts, platelet count, INR, fibrinogen, etc.) will also be assessed according to the study schedule.
- Physical examinations will be assessed according to the study schedule.
- According to the investigator's assessment, all clinically relevant changes in vital function and laboratory testing parameters findings will be considered AEs.

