9.1.3.1 Adverse Events

Adverse events will be coded and classified using MedDRA® terms (system organ class and preferred terms).

When a causal relationship of an AE is classified by the investigator as definitely or possibly related, the event will be defined as a suspected ADR. A suspected ADR with a causal relationship of “definitely related” will be defined as an AR. The sponsor will consider the investigator’s causality assessment and also provide its own assessment. If there is any disagreement in causality assessment between the investigator and the sponsor, a separate summary of suspected ADRs/ARs will be provided.

For summary purpose, AEs will be classified as treatment-emergent AEs (TEAEs) or non-TEAEs depending on the comparison of AE onset date/time with the start date/time of study treatment. A TEAE will be defined as an AE which occurs between the start of study treatment and the final visit of the clinical study. A non-TEAE will be defined as an AE which occurs prior to the start of study treatment. Non-TEAEs and TEAEs will be summarized separately.

In addition, TEAEs, including suspected ADRs, will be summarized by each treatment group, system organ class, preferred term, causal-relationship, severity, and seriousness (serious versus non-serious) using descriptive statistics. At each level of summarization, a

subject will only be counted once per system organ class or preferred term using the most severe AE or the AE with the strongest causal relationship to the treatment.

AEs (including suspected ADRs) temporally associated with PE-A 5% (ie, those occurring during a PE session or within 72 hours after the completion of a PE session) will be summarized by presenting incidences and percentages and listed.

Subjects with SAEs, AEs leading to death, or who withdraw from the study because of an AE will also be individually listed and summarized.

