- PT Rates – summary of the total number of plasma exchange sessions, , the total number of temporally associated adverse events and the rate per plasma exchange session, and the total number and rate of adverse events per week on the study by preferred term.. Rate per week on the study is defined as total number of events divided by total duration of weeks on the study . This summary applies to the SMT+PE-A 5% group only.

At each level of summarization, a subject will only be counted once per SOC or preferred term, using the most severe AE or the AE with the strongest causal relationship to the treatment as applicable. Summary tables will be sorted in descending frequency within the SMT+PE-A 5% group, then descending frequency with the SMT group, and then alphabetically.

The following table identifies the sets of adverse events that will be presented for each of these types of summaries.

Adverse Event Subset	TEAE Summary					Listing
	SOC / PT	PT	SOC / PT / Severity	SOC / PT / Causality	PT Rates*	
AEs with Onset Prior to Treatment	x					
TEAEs	X#		x	x	x	x
Suspected ADR	X#		x		x	
Non-Serious Suspected ADR	x					
Serious Suspected ADR	x					
AR	X#		x		x	
Non-Serious AR	x					
Serious AR	x					
TE SAEs	x			x		x
Non-serious TEAEs	x#					
TEAEs leading to Study Withdrawal	x					x
TEAEs leading to Death	x					x
Temporally Associated TEAEs*	x				x	

* This subset applies only to the SMT+PE-A 5% group.

This summary will include number of events by SOC / PT.

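### The SAP widens the main safety variable from the treatment period to the study period without declaring it, and plans no table of subjects with a suspected ADR in the protocol's window

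*SAP*

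**What the plan says.** The protocol synopsis and Protocol 8.1 name two main safety quantities: the number of suspected ADRs, and the "incidence rate of subjects with suspected ADRs during the treatment period and within 72 hours after PE-A 5% completion (or after PE-A 5% stops". The treatment period is bounded: "The Treatment Period will be up to 17 days" (Protocol 4.2). Subjects in both arms are "followed for 90 days after randomization".

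SAP 5.4.2 states the same variable as "incidence rates of subjects with suspected ADRs and ARs for the study period and within 72 hours after PE-A 5% completion". It keeps the 72-hour element and adds ARs, but the study period replaces the treatment period. Neither Section 12 nor the SAP version history mentions this. Section 12 does declare smaller safety changes, such as extra adverse event categories.

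SAP 10.1 builds its suspected ADR tables on treatment-emergent events, which SAP 6.1.6 runs from the start of study treatment to the final visit. It classifies causality by the investigator's assessment only. Protocol 9.1.3.1 starts from the same classification but adds a commitment: "If there is any disagreement in causality assessment between the investigator and the sponsor, a separate summary of suspected ADRs/ARs will be provided".

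**The concern.** The treatment period and the study period are different windows. The protocol's window captures reactions close to an invasive procedure. The SAP's captures anything judged related up to Day 90. If the SAP is followed as written, the clinical study report will give the subject incidence of suspected ADRs for the longer window and not for the one the protocol designates. A reader comparing the report with the protocol would find no notice of the switch.

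The missing causality summary matters because the trial is open-label (Protocol 4.3.3), so the investigator assigns relatedness knowing the arm. Protocol 8.3.4 already requires the sponsor to make its own assessment, and the disagreement summary is where the two would be compared.

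**Working it through.** There is no stated figure to reproduce. The check is a comparison of windows and a trace of the tables in SAP 10.1.

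**Step 1: where the protocol window ends in the PE-A 5% arm.** Protocol 6.1.1.3 gives the spacing: "Treatment schedule consists of 2 initial PE-A 5% sessions on consecutive days followed by every other day PE-A 5% sessions". Tables 6-1 and 6-2 put sessions on Days 1, 2, 4, 6, 8, 10, 12, 14 and 16, with 4 to 9 sessions per subject. Taking the treatment period to end with the last session, window end = day of last session + 3.

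| Sessions | Last session (day) | Window ends (day) | Days from there to Day 90 | 90 ÷ window end |
|---|---|---|---|---|
| 4 | 6 | 9 | 81 | 10.0 |
| 5 | 8 | 11 | 79 | 8.2 |
| 6 | 10 | 13 | 77 | 6.9 |
| 7 | 12 | 15 | 75 | 6.0 |
| 8 | 14 | 17 | 73 | 5.3 |
| 9 | 16 | 19 | 71 | 4.7 |

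**Step 2: whether the SAP's temporally associated window covers the same time.** SAP 10.1 defines it as during a session or within 72 hours of its completion. On-schedule sessions are at most 2 days = 48 hours apart, which is below 72, so the separate windows join into one running from the first session to 72 hours after the last. That equals the Step 1 window. If a session is missed, starts are 96 hours apart and up to about 96 − 72 = 24 hours are uncovered.

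**Step 3: what each planned table delivers.**
- Suspected ADR and AR by system organ class and preferred term, and by severity: number and percentage of subjects, but to the final visit.
- Temporally associated events by system organ class and preferred term: number and percentage of subjects in the window, but all causalities together and the PE-A 5% arm only.
- Preferred-term rates, ticked for Suspected ADR and AR: temporally associated event counts and a rate per session, plus a rate per week on study. These are events, not subjects, and for the PE-A 5% arm only.

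No table combines suspected ADR or AR, the protocol window, and number and percentage of subjects. SAP 5.4.2 itself names subject incidence within 72 hours, so SAP 10.1 does not fully deliver even the SAP's own statement.

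**Step 4: the SMT arm.** Protocol 4.2 and 6.1.2 give SMT subjects a treatment period of 7 days, extendable to 17. The temporally associated definition and the rate table exclude that arm, so it has no window-limited count.

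**Step 5: sensitivity to the meaning of treatment period.** Protocol 7.2.1.2 also describes it as Day 1 to Day 17. On that reading a 4-session subject's protocol window runs to Day 17 (90/17 = 5.3), while the temporally associated window still closes at Day 9. The rate table then misses 17 − 9 = 8 days. For 9 sessions, Day 19 still governs.

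**Step 6: the per-week rate.** The SAP defines it thus: "Rate per week on the study is defined as total number of events divided by total duration of weeks on the study". For E events all inside the window and follow-up to Day 90, the ratio of the in-window rate to the on-study rate is (E ÷ 9/7) / (E ÷ 90/7) = 10 with 4 sessions and 90/19 = 4.7 with 9. These are upper bounds: events after the window and deaths before Day 90 both reduce them.

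**The case against.** Three points stand on the other side.

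First, a reader might infer that the SAP drops the protocol's main safety variable altogether and that no table touches it. The documents do not support that. SAP 5.4.2 keeps the 72-hour element. The preferred-term rate table, read naturally, supplies window-limited suspected ADR event counts in the PE-A 5% arm, although the SAP does not spell out how its contents apply to each ticked subset. The all-causality table covers the same window, and every adverse event is listed, so the missing count is recoverable.

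Second, the whole-study tables are not an invention of the SAP. Protocol 9.1.3.1 itself summarises suspected ADRs among treatment-emergent events to the final visit, with temporally associated events, including suspected ADRs, summarised separately by incidence and percentage. The tension with Protocol 8.1 already exists inside the protocol. This explains the SAP's layout but does not remove the need for a table matching Protocol 8.1.

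Third, a reader might infer from Step 6 that the main safety result is understated up to tenfold. It is not. The main variable is a count of events and an incidence of subjects, and lengthening the window cannot lower either. The factors apply only to the per-week rate, which the SAP adds, in one arm. The per-session rate beside it is undiluted.

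It is also fair to say that the causality summary is a separate matter from the window, and that it is conditional on a disagreement arising. The commitment is still in the protocol, and the SAP neither plans for it nor declares its removal.

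**Conclusion.** The point holds in limited form. SAP 5.4.2 changes the window of the protocol's main safety variable without declaring it. SAP 10.1 leaves the number and percentage of subjects with a suspected ADR or AR in the treatment period plus 72 hours unplanned, and plans nothing window-limited for SMT. It also omits the summary for causality disagreement.

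The planned subject counts run 71 to 81 days past the protocol window for a PE-A 5% subject followed to Day 90, assuming on-schedule sessions and a treatment period that ends with the last one. The whole-study subject count will be at least as large as the window count. How much larger cannot be said, because the documents give no timing of ADRs. Efficacy conclusions and formal tests are untouched, since Protocol 9.1.3 makes safety comparisons descriptive. The change should be made because this is the designated main safety variable for an invasive procedure and the repair is small.

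**What to change.** - In SAP 5.4.2, restore the protocol window (treatment period and 72 hours after PE-A 5% completes or stops), and keep the whole-study summary as supportive.
- In SAP 10.1, add a suspected ADR and AR table limited to that window, with events and number and percentage of subjects. State whether the treatment period ends with the last session or at Day 17, and give the corresponding treatment-period window for SMT, where no exchange exists to start the 72 hours.
- Add the separate suspected ADR/AR summary for cases where sponsor and investigator causality differ.
- State that the preferred-term rate table applies its temporally associated count to each ticked subset, if that is intended.
- Declare any remaining departure from Protocol 8.1 or 9.1.3.1 in Section 12.

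The cost is SAP wording and a few descriptive tables. Protocol 8.3.8 already requires onset date and time and investigator causality in the eCRF, and Protocol 8.3.4 already requires the sponsor's assessment, so no new data are needed.
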